2.4.3. ALLOWED WINDOW OF EACH SCHEDULE

PHASE	Evaluation Schedule		
	Interval	Follow-Up Window	Months Post-Op Range
PHASE 1	Immediate Post-Op	± 2 weeks	Immediate post-op < 2 weeks
	6 weeks	± 2 weeks	4-8 weeks
	6 month follow-up	± 1 month	5-7 months
	1 year follow-up	± 2 months	10-14 months
	2 year follow-up	± 3 months	19-27 months
	3 year follow-up	± 3 months	33-39 months
PHASE 2	5 year follow-up	± 3 months	57-63 months
	7 year follow-up	± 3 months	81-87 months
	10 year follow-up	± 3 months	117 – 123 months

2.5. Randomization

Patients will be randomized to receive Delta Ceramic Head (investigational group), or CoCr Head (control group). Patients have an equal opportunity of being assigned to the investigational group or control group. Specifically:

In case of unilateral patients, the affected side of hip will be randomized to one of two groups. In case of bilateral patients, both sides of hip will be randomized to the same device (Delta Ceramic or CoCr).

The randomization will occur via a random number generator (manual or computer). Block randomization will be used. Blocks of K patients will be created where K = 4.

The possible sequences are AABB, BBAA, ABAB and BABA. Two sets of randomization blocks will be followed by unilateral and bilateral patients respectively.

For unilateral patients, A or B represents the device assigned to affected side of the hip. For bilateral patients, A or B represents the device assigned to both affected sides of the hip.

The doctor or other health care professional does not choose the participants for each group. For Patients satisfying inclusion criteria, randomization will occur by retrieving the next randomly generated group assignment.

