2. STUDY DESIGN

2.1. OVERALL DESIGN

This study is a prospective, multi-center randomized controlled study and will be conducted in Japan at a maximum of 5 sites.

The study will consist of two phases, over a period of 11 years. Phase 1 will collect data on penetration rate recognized as “early bedding-in” and patients will be followed at immediate post-op, 6 months and 1

year, 2 years, 3 years. Phase 2 will collect data on penetration rate recognized as “steady-state wear” after 5 years, 7years and 10 years post-op.

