2.4. ASSESSMENT PROCEDURE

2.4.1. ASSESSMENT PARAMETERS AND METHODS

Medical History and Demographic Data

Demographic information will be collected, a detailed medical history will be obtained and a physical examination will be performed (including height, weight).

Clinical Assessments

An operative record will be completed to record details of each operative procedure and of the used implants.

Data to determine the clinical and functional performance of the device will be collected. Pre-operative and post-operative analysis will be compared using recognized and validated systems (JOA Score).

Radiographic Assessments (including Radiographic Assessment protocol)

A radiographic assessments including polyethylene wear analysis and cup inclination angle will be completed at each follow-up period.

The X-rays must be taken according to the Martell technique*, which requires an A/P pelvis view centered over the pubis. See attachment for radiographic technique.

For the polyethylene wear analysis, all Radiographic images will be determined and the penetration rate will be measured by Hip Analysis Suite (software program, [name] at Chicago University).

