9. MONITORING PLAN

Prior to commencing the study Biomet Japan will provide the investigators with the necessary information to enable him/her to carry out his responsibilities. This information includes but not limited to:

- Investigator Brochure i.e. study protocol, investigator responsibilities, device information, etc.
- Ethical Committee Approval Information.
- Case Report Forms.
- Patient Consent Forms
- EDC user manual

The monitor of the evaluation periodically reviews the post-operative follow-up dates on all subjects for each evaluator. A follow-up schedule is then sent to each investigator, which illustrates any follow-up, reports which are due or missing. Every effort is made to assure that follow-up reports are completed in a timely manner, including contacting the evaluator by post, telephone or by personal visit when necessary. Also, during the course of the evaluation, the monitor will conduct periodic discussions with the investigator or staff to ensure that the evaluation is being conducted in accordance with the protocol. The monitor will maintain records of each visit or discussion.

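### Section 2.5 discloses a fixed block of 4, allows only four of the six balanced sequences and describes no concealment, so staff who know earlier allocations on a list can foresee later ones

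*Combined protocol and SAP*

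**What the plan says.** Section 2.5 sets equal allocation: "Patients have an equal opportunity of being assigned to the investigational group or control group". It fixes the block size, "Blocks of K patients will be created where K = 4", and lists the permitted orders: "The possible sequences are AABB, BBAA, ABAB and BABA". There are separate lists by laterality: "Two sets of randomization blocks will be followed by unilateral and bilateral patients respectively". Once a patient meets the inclusion criteria, "randomization will occur by retrieving the next randomly generated group assignment". The section adds that clinicians do not choose who goes into which group, and it leaves open whether the generator is manual or computerised.

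Three other sections bear on who can know what:

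- Section 9 lists the material supplied to investigators, including "Investigator Brochure i.e. study protocol, investigator responsibilities, device information, etc". The block size and sequences therefore reach the sites.
- Section 2.4.1 states: "An operative record will be completed to record details of each operative procedure and of the used implants". The head actually used is known and recorded at the site.
- Section 2.1 says the study "will be conducted in Japan at a maximum of 5 sites".

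The visible text does not say who generates or holds the lists, whether they are central or by site, or how the next assignment is hidden until a patient is committed. It does not mention blinding.

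**The concern.** Blocked randomization protects against selection only if the person enrolling cannot tell what comes next. Here the block length is public, the permitted orders are public and fewer than they need be, and earlier assignments are visible to the operating team. What remains unknown to a site is then only what it cannot see of the list, and the plan does not say how much that is.

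Staff who can foresee the next head can enrol, defer or decline a patient accordingly. The plan leaves room for this. Several relative contraindications in section 3.2 call for judgement, and section 3.3 lets the investigator withdraw a subject on professional judgement. Comparing wear with CoCr and Delta heads is a primary objective (section 1.4), and it relies on comparable groups. Demographics, medical history, height and weight are collected, so adjustment could reduce an imbalance in those. It could not remove selection on factors that were not measured.

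**Working it through.** **Inputs from the documents.** Block size 4, fixed; permitted sequences AABB, BBAA, ABAB, BABA; 1:1 allocation (all section 2.5). At most 5 sites (section 2.1). 160 hips (section 2.2).

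**Assumptions not in the documents.** The listed sequences are equally likely. The observer knows where each block starts. For a shared list, the *s* sites are of equal size and each sees only its own allocations, so any earlier position is visible with probability 1/*s*.

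**Step 1: the plan's own property.** At each of the four positions, two of the four listed sequences have A, so P(A) = 2/4 = 1/2. Equal allocation is reproduced. The plan gives no predictability figure to check.

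**Step 2: what is left out.** The number of balanced sequences of length 4 is C(4,2) = 6. Four are listed; ABBA and BAAB are missing.

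**Step 3: structure of the listed four.**

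| Positions 1–2 | Only possible positions 3–4 |
|---|---|
| AA | BB |
| BB | AA |
| AB | AB |
| BA | BA |

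Position 3 is always the opposite of position 2, and position 4 the opposite of position 1. One earlier allocation in the right place is enough to fix a later one. With all six sequences, no single earlier allocation does this.

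**Step 4: observer sees the whole list.** Probability that the best guess is right, by position:

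| | Pos. 1 | Pos. 2 | Pos. 3 | Pos. 4 | Mean | Share certain |
|---|---|---|---|---|---|---|
| Listed four | 0.5 | 0.5 | 1 | 1 | 75% | (1 + 1)/4 = 50% |
| All six | 0.5 | 0.667 | 0.667 | 1 | 70.8% | (1/3 + 1)/4 = 33.3% |

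With all six, position 3 is certain only when the first two match (1/3 of blocks). A fixed block of 2 gives 50% certain and 75% right, so the listed scheme is as predictable as that.

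**Step 5: one list shared by *s* equal sites.**

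- Listed four: position 3 is certain if position 2 was seen, and position 4 if position 1 was seen. Share certain = (1/*s* + 1/*s*)/4.
- All six: position 3 is certain if both earlier positions were seen and match, (1/*s*²)(1/3). Position 4 is certain if the two matching ones among the earlier three were both seen, 1/*s*². Share certain = (1/(3*s*²) + 1/*s*²)/4.

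| Sites on the list | Listed four | All six |
|---|---|---|
| 2 | (1/2 + 1/2)/4 = 25% | (1/12 + 1/4)/4 = 8.3% |
| 5 | (1/5 + 1/5)/4 = 10% | (1/75 + 1/25)/4 = 1.3% |

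With five sites, the best guess under the listed four is right (0.5 + 0.5 + 0.6 + 0.6)/4 = 55.0% of the time, against 54.4% with all six. All these figures fall if block starts are not known.

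**Step 6: in assignments.** If all 160 hips are unilateral, there are 160 assignments, of which 0.50 × 160 = 80 are certain (whole list seen) down to 0.10 × 160 = 16 (five sites, shared list). If 20% of patients were bilateral (an assumption), there are 160/1.2 = 133 assignments, of which 67 down to 13 are certain.

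**Step 7: alternatives, whole list seen.** Restoring ABBA and BAAB alone still leaves position 4 certain. With all permutations and block sizes of 4 and 6 chosen at random with equal probability, an observer who knows the two sizes but not their order is certain of 5.6% of assignments and guesses right 69.3% of the time (1,500 simulated lists of 160).

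**The case against.** The strongest reply is that the consequence is conditional. It requires knowledge of earlier allocations on the same list and of where blocks begin, and the plan does not say whether lists are shared. On a list shared by five sites, the best guess is right 55.0% of the time, close to a coin toss. Section 10.4 limits each doctor's database view to his own patients, which counts against any one clinician seeing a whole shared list through the study system. Even to an observer of a whole list, the first position of a block stays at 50/50, and so does the second under the listed sequences. Concealment may exist in practice or in appendices not seen here. The plan gives no reason why a surgeon would steer patients between heads.

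This fairly limits the size of the problem, and the range above reflects it. It does not remove the problem. The database restriction neither hides the next assignment nor prevents prediction on a by-site list, where a doctor's own patients may be most or all of the list.

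A second reply is that the remedy gains little on best guess: 75% to 69.3% for a whole list. That is correct. The gain is in certainty, which is what makes deliberate deferral possible, and there the fall is from 50% to 5.6%. Withholding block details and controlling release add protection that these figures do not count.

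Third, eligibility and consent before assignment are largely covered already by sections 2.5 and 10.3. What is new is a logged registration before the assignment is released. Fourth, recruitment is planned to last one year (section 2.6), so the change may come too late. The documents do not show recruitment status.

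**Conclusion.** The concern holds. Followed as written, section 2.5 makes the third and fourth assignments of every block certain to anyone who knows the first two. The share of assignments that can be foreseen with certainty runs from 50% (whole list seen) to 10% (one list shared by five equal sites), against 33.3% and 1.3% with all six sequences. These figures rest on equally likely sequences, known block starts and, for the lower end, equal sites that see only their own allocations.

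The 1:1 ratio is not affected. The harm is a risk of selection bias in a primary comparison; whether any occurs, and how large it is, cannot be estimated from the documents. The finding on concealment is that none is described, not that none exists. The point should be corrected: the weakness is plain in the text and the remedy is cheap.

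**What to change.** For all assignments not yet made, replace the two sentences in section 2.5 on the block size and the possible sequences with:

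> Randomly permuted blocks will be used, with all balanced sequences and randomly varied block sizes. Block sizes and sequences are held in a document not given to sites. Each assignment is released only after the patient has been registered as eligible and consented.

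Block sizes of 4 and 6 are one workable choice. State also who generates and holds the lists, and whether they are central or by site, since that decides how much any one site can foresee.

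The cost is a new list for the remaining assignments and a registration step before release. The downside is that an incomplete block of 6 can leave an imbalance of up to 3 patients per list, against up to 2 with blocks of 4.

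If enrolment has already closed, a new list changes nothing. In that case, record how the lists were held and released, and consider adjusting the wear comparison for the measured baseline factors, which is only a partial remedy.

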2.6. DURATION OF THE STUDY

Expected duration of recruitment period would be 1 year after the first case is enrolled. Each subject is to be followed-up to 3 years post-op for phase 1 and 10 years post-op for phase 2.

3. SELECTION AND WITHDRAWAL OF SUBJECTS

All subjects, regardless of sex, race, or geographic location, must fit into the scope of the Inclusion / Exclusion criteria to be eligible for the study. If required per applicable regulations, all participants must sign an Informed Consent to be enrolled into the study.

3.1. INCLUSION CRITERIA

In accordance with approved Indications for Use E1 liner and Delta Ceramic and CoCr femoral head hip system specifically:

Patients suitable for primary Total Hip Replacement

Patients with degenerative joint disease (inflammatory or non-inflammatory) or any of the composite diagnoses of:

- a. Osteoarthritis
- b. Avascular necrosis
- c. Legg Perthes
- d. Rheumatoid Arthritis
- e. Diastrophic variant
- f. Fracture of the pelvis
- g. Fused hip
- h. Slipped capital epiphysis
- i. Subcapital fractures
- j. Traumatic arthritis

Patients aged over 20

Patients with limited co-morbidity – ASA I – III

Patients must be able to understand instructions and be willing to return for follow-up

3.2. EXCLUSION CRITERIA

In accordance with approved Absolute and Relative Contraindications for use in participating countries for E1 liner and Delta Ceramic and CoCr femoral head hip system System.

Absolute contraindications include: infection, sepsis, and osteomyelitis.

Relative contraindications include:

- 1) uncooperative patient or patient with neurologic disorders who are incapable of following directions,
- 2) osteoporosis,
- 3) metabolic disorders which may impair bone formation,
- 4) osteomalacia,
- 5) distant foci of infections which may spread to the implant site,
- 6) rapid joint destruction, marked bone loss or bone resorption apparent on roentgenogram, and
- 7) vascular insufficiency, muscular atrophy, or neuromuscular disease.
- 8) pregnancy

3.3. SUBJECT WITHDRAWAL

It is recognized that the subject's participation in this trial is entirely voluntary, and that she/he may refuse to participate and may withdraw from participation at any time without jeopardy to any future medical care. It is also recognized that the investigator, at his/her discretion, may withdraw a subject from this study based upon his/her professional judgment. In event of subject withdrawal, applicable local procedures should be followed.

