2.3. PRIMARY AND SECONDARY ENDPOINTS

PHASE 1: Immediate post-op to 3 years	
Primary endpoints	Early bedding in
Secondary endpoints	At all follow-up visits: Survivorship up to 3 years JOA Radiographic Assessment Complications including revisions
PHASE 2: 5 to 10 years	
Primary endpoints	Steady-state wear
Secondary endpoints	At all follow-up visits: Survivorship up to 10 years JOA Radiographic Assessment Complications including revisions

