4. ADVERSE EVENT MANAGEMENT AND REPORTING

A record of all adverse events relating to subjected device (see Risk Analysis Section) and operative procedure, including details of the nature, onset, duration, severity, will be made on the

relevant section(s) of the subject's CRF. The subject will be questioned about any adverse event(s) at each subsequent follow-up assessment visit.

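### Discretionary investigator withdrawal, handled by local procedures, may lose revisions from 10-year survivorship while the implant stays in place

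*Combined protocol and SAP*

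**What the plan says.** Section 3.3 covers two kinds of withdrawal. Patients may leave at any time, which is not in question here. Separately, "the investigator, at his/her discretion, may withdraw a subject from this study based upon his/her professional judgment". It sets no criteria and asks for no recorded reason. On handling it says only "In event of subject withdrawal, applicable local procedures should be followed". Section 2.1 allows up to 5 sites.

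The endpoints in section 2.3 need long follow-up. Phase 2 has "Steady-state wear" as primary and "Survivorship up to 10 years" among the secondaries; phase 1 has survivorship to 3 years. Section 2.6 adds: "Each subject is to be followed-up to 3 years post-op for phase 1 and 10 years post-op for phase 2".

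On event capture, the schedule in section 2.4.2 lists complications, including revisions, at any time. Section 4 says "The subject will be questioned about any adverse event(s) at each subsequent follow-up assessment visit".

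On allocation, section 2.5 says "The doctor or other health care professional does not choose the participants for each group". That concerns assignment. No section describes masking of the investigator, patient, assessor or film reader.

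**The concern.** In a drug trial, an investigator's withdrawal often means stopping treatment. Here the femoral head and liner stay in the patient and the hip remains at risk of revision. The decision can change only what the study goes on to record. It is made by someone who can be expected to know the arm, since the operative record lists the implants used (section 2.4.1).

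If the decision is related to how the hip is doing, for example pain or suspected loosening, the withdrawn hips are more likely to be revised than those that stay. Survivorship estimates assume the opposite: that hips leaving observation carry the same later risk as those remaining. A breach of that assumption is informative censoring. It could make survivorship look better than it is and, if the habit differs between arms, distort the comparison of ceramic with cobalt-chrome heads. Under section 2.5 both hips of a bilateral patient receive the same head, so one such withdrawal removes two hips from one arm.

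**Working it through.** **Inputs from the documents (section 5.1, sample size).** N = 63 per group before loss, 20% loss over 10 years, 80 hips per group. No revision rate or investigator-withdrawal rate is given.

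**Assumed inputs.** True 10-year revision risk r = 5% (4 of 80), with a range of 3% to 10%. Share f of the hips due for revision that are withdrawn first: one half, and also one quarter.

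**Step 1: the plan's own allowance.** 63 / (1 − 0.20) = 78.75, rounded up to 79; the plan states 80, which agrees to within one hip. The allowance replaces numbers. It does nothing about which hips are lost.

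**Step 2: is a revision after withdrawal captured anywhere?**
- Section 2.4.2 records revisions at any time, so capture is not tied only to visits, but it does not mention withdrawn patients.
- Section 4 questions patients at follow-up visits, which a withdrawn patient no longer attends.
- Section 9 has the monitor pursue due or missing reports and does not mention withdrawn patients.
- The interim and final analysis paragraphs in section 5 give no analysis set, censoring rule or missing-data method.

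No section says that such a revision is collected or counted.

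**Step 3: effect on survivorship in one arm.**
- All 4 revisions observed: 1 − 4/80 = 95.0%.
- Two of those hips withdrawn first and dropped: 1 − 2/78 = 97.4%.
- Two withdrawn first and censored (Kaplan-Meier, no other losses): (77/78) × (76/77) = 76/78 = 97.4% if both withdrawals precede the two observed revisions, and 78/80 = 97.5% if both follow them.

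Dropping and censoring give nearly the same answer, so the choice of estimator does not remove the problem.

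**Step 4: range.** Apparent revision risk = r(1 − f) / (1 − rf).

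| True risk r | f = 1/4 | f = 1/2 |
|---|---|---|
| 3% | 2.3% | 1.5% |
| 5% | 3.8% | 2.6% |
| 10% | 7.7% | 5.3% |

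**Step 5: between arms.** If both arms have a true risk of 5% and the loss in step 3 occurs in one arm only, the arms read 95.0% and 97.4%. That is an apparent gap of 2.4 percentage points with no true difference.

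**Step 6: a ceiling for wear.** Suppose wear is normal with SD 0.07 (section 5.1, taken as mm) and the highest-wear fraction w of one arm has no usable wear value at all. The arm's mean falls by SD × φ(c)/(1 − w), where c is the normal quantile at 1 − w. For w = 5%, 10% and 20% the fall is 0.0076, 0.0136 and 0.0245. The last is about 5% of the printed 0.5 mm difference (0.0245/0.5). It would be 70% of 0.035 (0.0245/0.035), which is 0.5 SD, the difference at which N = 63 reproduces: 2 × (1.96 + 0.84)² / 0.5² ≈ 63, two-sided 5%, 80% power. That mismatch in the sample-size inputs is a separate matter. The scenario is extreme, because films taken before withdrawal would normally still contribute.

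**The case against.** The strongest case against runs as follows.

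- **The size and direction are assumed.** The documents give no revision or withdrawal rate, and nothing shows that investigators would withdraw failing hips. This stands: the bias is possible, not demonstrated.
- **There is mitigating text.** Revisions are scheduled at any time (2.4.2), the monitor pursues missing reports by post, telephone or visit (section 9), and source documents must record the subject's course (6.1). This shows that capture is not purely visit-based. None of it says what happens once a patient has been withdrawn.
- **The wear effect is weaker.** Wear is measured by software (2.4.1), the documents do not say that surgeons see individual results, and nothing says that earlier films are discarded. This stands, and wear is a lesser part of the point.
- **The surgeon's knowledge of the head cannot be designed away.** True. It is a reason to narrow the discretion, not a separate fault.
- **The case report forms and consent form were not available for review.** They may record a reason for withdrawal or already cover later data use. This stands, so the consent change is conditional.
- **Patient-initiated withdrawal and ordinary loss can be just as informative.** True, and an analysis rule for those is also needed. The investigator clause is still the one that the protocol itself controls.

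A reader might also infer from the sample-size section that up to 80 − 63 = 17 hips per arm could be lost in this way. The documents do not support that. The 20% allowance covers loss from any cause; 20% of 80 is 16, and 17 partly reflects rounding 78.75 up to 80. In an example with 4 true revisions, at most 4 could be hidden.

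**Conclusion.** The point holds as a weakness in the withdrawal rule that should be corrected. Section 3.3 permits investigators to end outcome collection at discretion, under handling that may differ by site, for an intervention that cannot be stopped. No section provides for revisions to be collected or counted afterwards. Survivorship to 3 and 10 years is the endpoint mainly exposed; wear is exposed less, through missing later films.

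The size is illustrative: 95.0% reading as 97.4%, assuming 4 true revisions in 80 hips, 2 of them withdrawn first, and no later capture. A reader might go further and infer that survivorship will be overstated, that wear will be understated, or that one arm will be favoured. The text makes these possible but does not establish any of them. Nor do the documents declare the trial open-label; they simply describe no masking.

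**What to change.** In section 3.3, state that:

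- the investigator may stop study visits for a patient, with the reason recorded;
- unless the patient withdraws consent for data use, revision status and revision date continue to be collected to 10 years, from records or by telephone, and are counted in the randomised arm;
- this applies at all sites, subject to local ethics and regulatory requirements, in place of the general reference to local procedures;
- later pelvis films are used for wear only when they meet the radiographic technique in section 2.4.1.

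The cost is a protocol amendment with ethics committee approval (section 10.2), a consent line if the current form does not already cover it, and a little follow-up by existing site staff for withdrawn patients. No additional visits or imaging are required.
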